8.6.2 Secondary efficacy variables

The secondary efficacy endpoints of the study are:

- **Immunological Response 2:** Relative (%) change from baseline in the % of aberrant IELs vs intestinal epithelial cells (IECs)
- **Histological Response:** Relative (%) change from baseline in small intestinal villous height to crypt depth (VH:CD) ratio, Marsh score and total IEL counts
- **Clinical response:** Change from baseline in clinical symptoms
 - Bristol Stool Form Scale (BSFS)
 - Gastrointestinal Symptom Rating Scale (GSRS), including the celiac disease GSRS (CeD-GSRS)

Immunological Response 2: Relative (%) change from baseline in the % of aberrant IELs vs intestinal epithelial cells (IECs)

Immunological response 2 will be calculated as

(% of aberrant IELs by flow-cytometry) · (% total IEL vs IEC by immunochemistry).

Immunological response 2 will be analysed using the same method as for the primary endpoint, i.e. the following model will be fitted:

$$Y_{ij} = \mu + \beta \cdot \text{baseline \% IEL vs IEC}_{ij} + \alpha_j + \varepsilon_{ij},$$

where

Y_{ij} is the relative (%) change from baseline in the % of aberrant IELs vs intestinal epithelial cells for subject i ($i = 1, \dots, n_j$) from treatment group j ($j = 1, 2$),

μ is the overall mean,

β is the parameter estimate of baseline % IELs vs IEC by flow-cytometry,

α_j is the fixed effect due to treatment j ,

ε_{ij} is the random error for subject i from treatment group j ; $\varepsilon_{ij} \sim N(0, \sigma_\varepsilon^2)$.

The following SAS code will be used to fit the above-specified model:

```
proc glm data=IEL alpha=0.05 outstat=F_tests;
  class trt;
  model IEL_change = bl_IEL trt / clparm solution SS1 SS2;
  estimate "AMG 714 vs Placebo" trt 1 -1;
  lsmeans trt /cl stderr;
  ods output ParameterEstimates=Par_est LSMeans=LS_meanCL
              LSMeans=LS_mean OverallANOVA=ANOVA Estimates=Eff_est;
run;
```

The modelling results (ANOVA table, parameter estimates, estimated treatment effect, marginal (i.e. least squares) means estimates and results of the check of assumptions) will be tabulated and 95% confidence intervals added, where appropriate.

As a secondary assessment, the same model will be fitted using the absolute change in % of aberrant IELs vs intestinal epithelial cells as a response variable. The modelling results (ANOVA table, parameter estimates, estimated treatment effect, marginal (i.e. least squares) means estimates and results of the check of assumptions) will be tabulated and 95% confidence intervals added, where appropriate.

The baseline and post-baseline values along with the change from baseline values (both relative and absolute) will also be described by summary statistics and tabulated by treatment group. Baseline and post baseline values will also be listed.

A frequency table by treatment group will be used to summarize the percentage of patients with at least 20% reduction from baseline in the % of aberrant IELs vs intestinal epithelial cells based on the second biopsy after Week 6.

PP population will be used for the analysis.

Histological Response: Relative (%) change from baseline in small intestinal villous height to crypt depth (VH:CD) ratio

Percent change from baseline in small intestinal villous height to crypt depth (VH:CD) ratio will be analysed using the same method as for the primary endpoint, i.e. the following model will be fitted:

$$Y_{ij} = \mu + \beta \cdot \text{baseline VH:CD}_{ij} + \alpha_j + \varepsilon_{ij},$$

where

Y_{ij} is the relative (%) reduction from baseline in the VH:CD ratio for subject i ($i = 1, \dots, n_j$) from treatment group j ($j = 1, 2$),

μ is the overall mean,

β is the parameter estimate of baseline VH:CD ratio,

α_j is the fixed effect due to treatment j ,

ε_{ij} is the random error for subject i from treatment group j ; $\varepsilon_{ij} \sim N(0, \sigma_\varepsilon^2)$.

The following SAS code will be used to fit the above-specified model:

```
proc glm data=IEL alpha=0.05 outstat=F_tests;  
  class trt;  
  model VHCD_change = bl_VHCD trt / clparm solution SS1 SS2;  
  estimate "AMG 714 vs Placebo" trt 1 -1;  
  lsmeans trt /cl stderr;  
  ods output ParameterEstimates=Par_est LSMeanCL=LS_meanCL  
             LSMeans=LS_mean OverallANOVA=ANOVA Estimates=Eff_est;  
run;
```

The modelling results (ANOVA table, parameter estimates, estimated treatment effect, marginal means estimates and results of the check of assumptions) will be tabulated and 95% confidence intervals added, where appropriate.

As a secondary assessment, the same model will be fitted using the absolute change in VH:CD as a response variable. The modelling results (ANOVA table, parameter estimates, estimated treatment effect, marginal (i.e. least squares) means estimates and results of the check of assumptions) will be tabulated and 95% confidence intervals added, where appropriate.

The baseline and post-baseline values along with the change from baseline values (both relative and absolute) will also be described by summary statistics and tabulated by treatment group. Baseline and post baseline values will also be listed.

The analysis will also include a frequency table by treatment group to summarize the percentage of patients with at least 30% improvement from baseline in VH:CD based on the second biopsy after Week 6.

PP population will be used for the analysis.

Histological Response: Change from baseline in Marsh score

Marsh-Oberhuber classification (Marsh, 1992; Oberhuber, 2000) i.e. the Marsh score, a commonly used histological score with possible values 0, 1, 2, 3a, 3b, 3c with 0 being the best and 3c the worst, will be assessed at screening and Week 12 biopsies.

The Marsh scores will be analysed using a simple logistic regression model, where improvement from baseline in the Marsh score is used as dependent variable and treatment group will be included in the model as explanatory variable. For modelling purposes, a binary variable with values 1 (in case improvement in Marsh scores, i.e. any decrease in score from baseline to Week 12, was observed) and 0 (no improvement in Marsh scores) will be used as a response. Logit function will be used as the link function. The following model will be fitted:

$$\log\left(\frac{p_j}{1-p_j}\right) = \mu + \alpha_j,$$

where

$Y_j \sim \text{Bin}(p_j, n_j)$ – is the number of subjects with improvement in Marsh scores by Week 12 in treatment group j ($j = 1, 2$),

p_j is the probability of improvement in Marsh score for subjects in treatment group j by Week 12,

μ is the overall mean (on logit scale),

α_j is the fixed effect due to treatment j on the logit scale.

The odds ratio for AMG 714 vs placebo groups will be reported and the following formula will be used for obtaining the ratio:

$$OR = \exp(\alpha_{AMG\ 714} - \alpha_{placebo}),$$

where $\alpha_{AMG\ 714}$ denotes the treatment effect of AMG 714 on logit scale and $\alpha_{placebo}$ denotes the placebo effect on logit scale.

The following SAS code will be used to fit the above-specified model:

```
proc genmod data=marsh descending;
  class trt;
  model marsh_imp = trt / dist=bin link=logit lrci type3;
  estimate 'OR AMG vs PLA ' trt 1 -1 / exp ;
  lsmeans trt /cl ilink;
  ods output ParameterEstimates=Par_est Estimates=Eff_est
             Type3=Type3
             LSMeans=Ls_mean;
run;
```

The modelling results (parameter estimates, estimated odds ratio of AMG 714 vs placebo, marginal (i.e. least squares) means estimates for treatment groups) will be tabulated and 95% confidence intervals added, where appropriate. Odds ratio and marginal means estimates for the probabilities will be presented on the original (probability) scale.

The baseline and post-baseline frequencies of all categories of the Marsh score scale, along with change from baseline frequencies will be tabulated by treatment group. Baseline and post baseline values will also be listed.

The analysis will also include the percentage of subjects with complete remission of the histological abnormalities according to the Marsh score, i.e., the % of subjects with Marsh scores 0-1. Frequency table by treatment group will be used for summarizing these results.

PP population will be used for the analysis.

Histological Response: Relative (%) change from baseline in total IEL counts

Change from baseline in total IEL counts (i.e., density of IELs by IHC) will be analysed using the same method as for the primary endpoint, i.e. the following model will be fitted:

$$Y_{ij} = \mu + \beta \cdot \text{baseline IEL}_{ij} + \alpha_j + \varepsilon_{ij},$$

where

Y_{ij} is the relative (%) reduction from baseline in the total IEL counts for subject i ($i = 1, \dots, n_j$) from treatment group j ($j = 1, 2$),

μ is the overall mean,

β is the parameter estimate of baseline total IEL count,

α_j is the fixed effect due to treatment j ,

ε_{ij} is the random error for subject i from treatment group j ; $\varepsilon_{ij} \sim N(0, \sigma_\varepsilon^2)$.

The following SAS code will be used to fit the above-specified model:

```
proc glm data=IELc alpha=0.05 outstat=F_tests;
  class trt;
  model IELc_change = bl_IELc trt / clparm solution SS1 SS2;
  estimate "AMG 714 vs Placebo" trt 1 -1;
```

```
lsmeans trt /cl stderr;  
ods output ParameterEstimates=Par_est LSMeanCL=LS_meanCL  
LSMeans=LS_mean OverallANOVA=ANOVA Estimates=Eff_est;  
run;
```

The modelling results (ANOVA table, parameter estimates, estimated treatment effect, marginal means estimates and results of the check of assumptions) will be tabulated and 95% confidence intervals added, where appropriate.

As a secondary assessment, the same model will be fitted using the absolute change in total IEL counts as a response variable. The modelling results (ANOVA table, parameter estimates, estimated treatment effect, marginal (i.e. least squares) means estimates and results of the check of assumptions) will be tabulated and 95% confidence intervals added, where appropriate.

The baseline and post-baseline values along with the change from baseline values both relative and absolute) will also be described by summary statistics and tabulated by treatment group. Baseline and post baseline values will also be listed.

PP population will be used for the analysis.

Change from baseline in clinical symptoms: Bristol Stool Form Scale (BSFS)

The Bristol Stool Form Scale is a pictorial aid to help subjects identify the shape and consistency of their bowel movements during the study (Riegler *et al* 2001).

Subjects will be asked to complete this form daily using an electronic diary at the time of each bowel movement from randomization through the Final Study Visit (Visit 9; Week 16/Day 112). If no bowel movements were experienced by the subject on any given day, the subject should document this using the electronic diary.

BSFS will be described by calculating daily and weekly number and type of bowel movements.

The total weekly bowel movement counts will be analysed using generalized linear mixed models with subject as a random effect. The statistical model will include as fixed effects treatment group, time (week) and their interaction. Poisson distribution with log-link will be used for modelling the counts. The following model will be fitted:

$$\log(Y_{ijk}) = \mu + \alpha_j + \gamma_k + \lambda_{jk} + \eta_i + \varepsilon_{ijk},$$

where

- Y_{ijk} is the bowel movement count for subject i ($i = 1, \dots, n_j$) from treatment group j ($j = 1, 2$) at week k ($k = 0, 1, \dots, 16$),
- μ is the overall mean on log-scale,
- α_j is the fixed effect due to treatment j on log-scale,
- γ_k is the fixed effect due to week k on log-scale,
- λ_{jk} is the fixed interaction effect due to treatment j and week k on log-scale,

Weekly bowel movements and their BSFS types will be tabulated by treatment group and week and summarized by descriptive statistics, absolute numbers and percentages. Also, percentage of subjects with diarrhoea (at least 1 BSFS ≥ 6 for the week) and percentage of subjects with constipation (at least 3 days without bowel movement for the week) by week and by treatment group will be presented. Mean weekly bowel movement counts will also be presented graphically by time point and treatment group.

As an exploratory assessment, averages by treatment for proportion of subjects showing BSSF ≥ 6 by time will be plotted. The differences in treatment AUCs will be explored using one-way analysis of variance. These analyses will be conducted internally by Celimmune.

The daily bowel movement counts and their BSFS scores will only be listed.

ITT population will be used for the analysis as long as there is a baseline and post-treatment measure (i.e. not lost to follow-up).

Change from baseline in clinical symptoms: Gastrointestinal Symptom Rating Scale (GSRs)

The GSRs is a 15-question 7-scale questionnaire used to assess five dimensions of gastrointestinal syndromes: diarrhea, indigestion, constipation, abdominal pain and reflux (Svedlund *et al* 1988). While not specific for celiac disease, the GSRs is widely used in gastroenterology and has been used in several clinical trials of experimental medications in celiac disease, thus becoming a very useful tool with abundant existing reference data (Kelly *et al* 2013; Lähdeaho *et al*, 2011; Leffler *et al*, 2015).

Subjects will be asked to complete this questionnaire weekly, using an electronic diary, from the day of randomization through the Final Study Visit (i.e. on Visits 1 to 9).

The total GSRs score will be calculated as the mean of the scores of all 15 questions, with the scores for the individual questions between 1 (No discomfort at all) and 7 (Very severe discomfort). Therefore, the smaller the total GSRs score, the milder the symptoms of the subject.

The change from baseline in total GSRs score will be analysed using a linear mixed effects repeated measures model (MMRM) with the baseline value, treatment group, time point and a time point-by-treatment group interaction term as fixed effects with an underlying correlation structure between the time points that results in the best fit for the model. Subject will be included as a random effect. The following model will be fitted:

$$Y_{ijk} = \mu + \alpha_j + \gamma_k + \lambda_{jk} + \beta \cdot \text{baseline GSRs}_{ij} + \eta_i + \varepsilon_{ijk},$$

where

Y_{ijk} is the absolute change from baseline in total GSRs score for subject i ($i = 1, \dots, n_j$) from treatment group j ($j = 1, 2$) at week k ($k = 1, 2, \dots, 16$),

μ is the overall mean,

The baseline and post-baseline total GSRS scores along with the change from baseline values will also be described by summary statistics and tabulated by treatment group. In addition to that, the baseline and post-baseline scores of all 15 questions and for the mean total scores of five dimensions of gastrointestinal syndromes (diarrhoea (questions 11, 12 and 14), indigestion (questions 6-9), constipation (questions 10, 13 and 15), abdominal pain (questions 1, 4 and 5) and reflux (questions 2 and 3)) along with the change from baseline values will be described by summary statistics and tabulated by treatment group. Both the scores of individual questions and the total GSRS scores will also be listed. Mean total GSRS scores as well as the scores of the individual questions, will also be presented graphically by time point and treatment group.

ITT population will be used for the analysis as long as there is a baseline and post-treatment measure (i.e., not lost to follow-up).

Change from baseline in clinical symptoms: the celiac disease GSRS (CeD-GSRS)

The CeD-GSRS is formed by the subset of questions from GSRS questionnaire (questions 1, 4-9, 11, 12 and 14).

The total CeD-GSRS score is calculated as the mean of scores of all 10 questions in CeD-GSRS questionnaire, with the scores of the questions between 1 (No discomfort at all) and 7 (Very severe discomfort). Therefore, the smaller the total CeD-GSRS score, the milder the symptoms of the subject.

The change from baseline in CeD-GSRS will be analysed using a linear mixed effects repeated measures model (MMRM) with the baseline value, treatment group, time point and a time point-by-treatment group interaction term as fixed effects with an underlying correlation structure between the time points that results in the best fit for the model. Subject will be included as a random effect. The following model will be fitted:

$$Y_{ijk} = \mu + \alpha_j + \gamma_k + \lambda_{jk} + \beta \cdot \text{baseline CeD GSRS}_{ij} + \eta_i + \varepsilon_{ijk},$$

where

Y_{ijk} is the absolute change from baseline in total CeD-GSRS score for subject i ($i = 1, \dots, n_j$) from treatment group j ($j = 1, 2$) at week k ($k = 1, 2, \dots, 9$),

μ is the overall mean,

α_j is the fixed effect due to treatment j ,

γ_k is the fixed effect due to time point k ,

λ_{jk} is the fixed interaction effect due to treatment j and time point k ,

β is the parameter estimate of the baseline total CeD-GSRS score,

η_i is the random effect due to subject i ,

ε_{ijk} is the random error for subject i from treatment group j for time point k .

Due to the repeated structure of the data, the measurements within a subject will be correlated. Therefore, it is assumed that the overall covariance matrix of the response is block-diagonal. In order to determine the covariance structure that best fits the data, the same model with different covariance structures is fitted. Initially, models will be fit

assuming unstructured (UN) variance-covariance structure. Common within and between treatment variance components (compound symmetry (CS), first-order autoregressive (AR(1)) and Toeplitz covariance structures) will be further explored to increase sensitivity of statistical tests. The best model will be chosen by comparing the Akaike Information Criterion (AIC) of the models with different covariance structures.

The following SAS program will be used for carrying out the analysis:

```
proc glimmix data=ced_gsrs;
  class subjid trt week (ref=FIRST);
  model ced_gsrs = ced_gsrs_b1 trt week trt*week / solution;
  random _residual_ / subject=subjid type=UN;
  estimate "AMG 714 vs Placebo" trt 1 -1 /alpha=0.05 cl;
  estimate "Week 1: AMG 714 vs Placebo" trt 1 -1
    trt*week 0 0 0 0 0 0 0 0 0 0 0 0 0 0 0 0 1
    0 0 0 0 0 0 0 0 0 0 0 0 0 0 0 -1 /alpha=0.05 cl;
  estimate "Week 2: AMG 714 vs Placebo" trt 1 -1
    trt*week 1 0 0 0 0 0 0 0 0 0 0 0 0 0 0 0 0
    -1 0 0 0 0 0 0 0 0 0 0 0 0 0 0 0 /alpha=0.05 cl;
  ...
  estimate "Week 16: AMG 714 vs Placebo" trt 1 -1
    trt*week 0 0 0 0 0 0 0 0 0 0 0 0 0 0 0 1 0
    0 0 0 0 0 0 0 0 0 0 0 0 0 0 0 -1 0 /alpha=0.05 cl;
  lsmeans trt /alpha=0.05 cl;
  lsmeans trt*week /alpha=0.05 cl;
ods output CovParms=Cov_Par LSMeans=LS_est Estimates=Eff_est
  FitStatistics=Fit_Stat ParameterEstimates=Par_est
  Tests3=Type_3;
run;
```

Note that the value of `type` will be changed according to which covariance structure is being fitted.

The modelling results (parameter estimates, covariance parameter estimates, estimated treatment effect, marginal means estimates and results of the check of assumptions) will be tabulated and 95% confidence intervals added, where appropriate. If the parametric assumptions are not met, then in addition to the above-specified model, a generalized estimating equation (GEE) approach will be used as well.

The baseline and post-baseline total weekly CeD-GSRS scores along with the change from baseline values will also be described by summary statistics and tabulated by treatment group. The total weekly CeD-GSRS scores will also be listed. Mean total weekly CeD-GSRS will also be plotted by time point and treatment group.

ITT population will be used for the analysis.

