22.6 SECONDARY ENDPOINTS

Secondary endpoints will be described in the SAP and will include:

- Immunological Response 2: Reduction from baseline in the % of aberrant IELs vs intestinal epithelial cells
- Histological Response: improvement from baseline in small intestinal VH:CD ratio score, Marsh score and total IEL counts
 - VH:CD ratio by validated morphometry. Includes the % of patients with histological remission (VH:CD > 2).
 - Marsh-Oberhuber classes, Marsh 0, 1, 2, 3a-c. Grouping by converting the morphometric results into Marsh classes (Mäki-Jilab converter). Includes the % of patients with histological remission (Marsh 0-1).
 - IEL: for mucosal inflammation the density of IELs/100 epithelial cells will be calculated. The analysis will also include the percentage of patients with normalization of IEL counts vs. epithelial cells (% IELs < 50%).

- Clinical response: change from baseline in symptoms,
 - BSFS and number bowel movements by day and week
 - GSRS and CeD-GSRS, by week

In general, efficacy measures which require pre- and post-treatment biopsies will be based on the PP population (at least 2 biopsies, the second at least on Week 6 or later). Continuous variables will be analyzed based on the ITT population.

Change from baseline of Immunological Response 2, VH:CD and of total IEL counts will be analyzed using the same method as for the primary endpoint.

The Marsh scores will be analyzed using a multinomial logistic regression model, where treatment group, baseline Marsh score, and a treatment group-by-baseline Marsh score interaction term will be included in the model.

The secondary variable BSFS will be analyzed by calculating daily and weekly number and type of bowel movements. The bowel movement counts will be analyzed using generalized linear mixed models with subject as random effect. The statistical model will also include treatment group, time (week) and their interaction. The change in the weekly BSFS scores will mainly be assessed with descriptive statistics, where change from the 'normal (mid-scale)' will be explored. The GSRS and the CeD-GSRS will be analyzed using a linear mixed effects repeated measures model (MMRM) with the baseline value, treatment group, time point and a time point-by-treatment group interaction term as fixed effects with an underlying correlation structure between the time points that results in the best fit for the model. Subject will be included as a random effect.

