where $\mu_{AMG\ 714}$ and $\mu_{placebo}$ denote the mean baseline to Week 12 relative (%) change in % aberrant IELs vs total IELs as assessed by flow-cytometry in the AMG 714 and placebo arm, respectively. The hypotheses will be tested using a two-sided, 0.10 level of significance.

7 Estimation of sample size

The CELIM-RCD-002 study is an exploratory proof-of-concept (POC) study of an experimental medication, AMG 714, in RCD-II patients. While it will be the first such study sponsored by a pharmaceutical company, the straightforward design is based on several academic studies (Goerres *et al*, 2003; Brar *et al*, 2007; Tack *et al*, 2011a, 2011b) as well as on the nonclinical proof-of-principle signal obtained with AMG 714 in intestinal explants from patients with RCD-II (Malamut *et al*, 2010).

The sample size is based on the size of previous academic studies. Published prospective academic studies have ranged from 13 to 18 subjects total (Tack *et al*, 2011a, 2011b) and CELIM-RCD-002 will be the largest prospective trial ever conducted in RCD-II, a very rare malignant disease.

The sample size of 24 subjects (16 subjects in AMG 714 arm and 8 subjects in placebo arm) has been calculated to achieve at least ~ 80% power to detect a 20 percentage point difference in the primary endpoint, the difference in the baseline-to-Week 12 reduction of % aberrant IELs vs total IELs between the AMG 714 arm and placebo arm.

This sample size calculation was based on the following assumptions:

- Two-sided type one error rate $\alpha = 0.1$.
- Power $1-\beta = 0.8$.
- Analysis method: one-way analysis of variance (ANOVA) by SAS[®] (proc power).
- 2:1 allocation ratio between the AMG 714 and placebo arms.
- Common SD = 17.4 for the baseline to Week 12 reduction in % aberrant IELs as assessed by flow-cytometry.

- Mean change of 20 percentage points and 0 percentage points in the baseline to Week 12 reduction in % aberrant IELs in the AMG 714 and placebo arms, respectively.

The standard deviation used for the sample size calculation is computed from the % aberrant IELs (obtained by flow-cytometry) data from 13 subjects treated with cladribine (subset of the subjects reported in Tack et al, 2011).

8 Statistical methods

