8.2 General statistical considerations

Descriptive statistics (e.g. mean, median, standard deviation (SD), minimum (MIN), maximum (MAX), and number of subjects with an observation (N) or missing observation (NMISS)) are used for summarizing continuous variables. Additional statistics will be provided for PK-related data, including the geometric mean, SD of log-transformed data, geometric CV% and geometric N (i.e. number of subjects with an observation that are included in the natural logarithmic transformation).

Frequencies and percentages are used for summarizing categorical variables.

All summary statistics will be presented by treatment arm and if repeated measures, then by visit/collection time point.

All listings will be created using ITT population. The PP and ITT flags for each subject will be included in all listings.

All tests will be two-sided, if not stated differently. P-values smaller than 0.1 (for primary hypothesis) or 0.05 (all other hypotheses) will be considered statistically significant. In addition to the inferential statistics, 90% or 95% confidence intervals will be constructed. For the primary endpoint a 90% confidence interval of the treatment difference will be

constructed. Ninety-five percent (95%) confidence intervals will be constructed for the individual treatment point estimates.

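### SAP 8.6.2 tabulates an unexplained 30% relative gain in VH:CD in place of the protocol's VH:CD > 2 remission rate, leads with relative change, and words the model outcome as a reduction

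*SAP*

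**What the plan says.** Protocol 22.6 lists VH:CD by validated morphometry among the secondary endpoints and attaches one responder measure to it: "Includes the % of patients with histological remission (VH:CD > 2", that is, a ratio above 2. It asks for change from baseline by the same ANCOVA as the primary endpoint and does not say whether that change is relative or absolute.

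SAP section 2 reserves relative (%) change for the primary endpoint and says that VH:CD is evaluated by change from baseline. SAP 8.6.2 then leads with relative (%) change for VH:CD. It fits the same model to absolute change as a secondary assessment and adds a frequency table of the "percentage of patients with at least 30% improvement from baseline in VH:CD". The remission rate above 2 is not in that section.

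In the model definition for VH:CD, Y "is the relative (%) reduction from baseline in the VH:CD ratio for subject". For total IEL counts, Y "is the relative (%) reduction from baseline in the total IEL counts for subject". SAP 8.2.1 defines relative change as post-baseline minus pre-dose, divided by pre-dose, and both section headings say change.

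**The concern.** A responder measure that the protocol commits to is missing from the section that should carry it. The measure tabulated there answers a different question: proportional gain, not arrival at a remission threshold. A reader of the study report could take the 30% rate for the histological response rate that the protocol describes.

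The scale also matters. VH:CD is a ratio that can be close to 0 in flat mucosa. A fixed percentage then asks for very different amounts of recovery in different subjects, and relative change cannot be computed from a baseline of 0. The Marsh scale used in the trial runs to 3c, and the entry criteria set no lower limit on VH:CD, so low baselines are possible.

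Finally, benefit is an increase for VH:CD and a decrease for IEL counts. If Y is a reduction in the model text and a change elsewhere, the sign of the AMG 714 versus placebo estimate depends on which definition is programmed.

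**Working it through.** **The plan's own figure.** No sample size or power is stated for VH:CD. The only planning figure is for the primary endpoint: "The sample size of 24 subjects (16 subjects in AMG 714 arm and 8 subjects in placebo arm"), difference 20, SD 17.4, two-sided alpha 0.10. A noncentral t calculation gives 82.3% power at 16 + 8 and 77.3% at 14 + 7, so 24 reproduces. It has no bearing on VH:CD.

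**30% gain against the threshold of 2.** Inputs: the 30% cut-off (SAP 8.6.2), the threshold of 2 (Protocol 22.6), and illustrative baselines, since the documents give none. Gain needed = 0.30 × baseline. Value reached = 1.30 × baseline. Relative gain needed to reach 2 = (2 − baseline)/baseline.

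| Baseline | 30% gain | Value reached | Gain needed to reach 2 |
|---|---|---|---|
| 0.2 | 0.06 | 0.26 | 900% |
| 0.5 | 0.15 | 0.65 | 300% |
| 1.0 | 0.30 | 1.30 | 100% |
| 1.5 | 0.45 | 1.95 | 33.3% |
| 1.6 | 0.48 | 2.08 | 25% |

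The measures cross at 2/1.3 = 1.54. Below that baseline a subject can respond by the 30% rule and still miss 2. Between 1.54 and 2 the reverse can happen: from 1.6, any gain just over 25% passes 2 but is not a 30% response. The 30% rule also counts 0.2 to 0.26 as a response but not 1.5 to 1.9 (0.4/1.5 = 26.7%). None of this needs an assumption about noise.

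**Behaviour near 0.** A gain of 0.1 units is 10% from a baseline of 1.0 and 100% from 0.1. At 0 the formula in SAP 8.2.1 divides by 0.

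**Reading error (assumptions; the documents give no figure).** Let there be no true change, let b be the baseline and s the error SD of each biopsy. The chance of an apparent 30% gain is 1 − Φ(0.3b/(s√2)).

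| Baseline | Constant error, s = 0.1 | Constant error, s = 0.2 |
|---|---|---|
| 0.2 | 33.6% | 41.6% |
| 0.5 | 14.4% | 29.8% |
| 1.0 | 1.7% | 14.4% |
| 1.5 | 0.1% | 5.6% |

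This formula holds the threshold at the true baseline. Simulating error in both biopsies gives about 18–32% at 0.5 and 3–18% at 1.0 for the same SDs. If error is instead proportional to the baseline, s = c·b, the formula becomes 1 − Φ(0.3/(c√2)). That is 1.7% for c = 0.10 and 14.4% for c = 0.20 at every baseline, so the excess at low baselines disappears.

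**Direction.** A move from 1.0 to 1.3 is a change of +30% and a reduction of −30%. Fitting the ANCOVA to one simulated data set with the outcome sign reversed turned the treatment estimate from 17.9 to −17.9 and left the two-sided p-value at 0.239. SAP 8.2 makes tests two-sided unless stated otherwise, with "P-values smaller than 0.1 (for primary hypothesis) or 0.05 (all other hypotheses) will be considered statistically significant".

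**The case against.** Much is already covered. The absolute-change ANCOVA is planned, both forms of change are tabulated, and baseline and post-baseline values are listed, so the rate above 2 can be derived. A Marsh 0–1 remission rate is kept, and the 30% table is descriptive. The central reading is blinded, uses validated morphometry and treats biopsies with fewer than 3 measurable villus-crypt units as not evaluable. Relative change is the SAP's lead scale for the other continuous biopsy endpoints too. Protocol 13.1 rests the go/no-go decision on the two Immunological Responses, and 13.2 concedes that the study may be too short for histological recovery. All of this stands and limits the stakes.

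Three stronger readings are tempting and are not supported:

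- A reader might infer that 30% is a trivial gain, or that the rate would mostly be reading noise. That needs low baselines and constant additive error, and the documents give neither. For previously treated subjects, entry requires only Marsh ≥ 1, so severe atrophy is not a given.
- A reader might infer that the VH:CD analysis runs in the wrong direction. It is a wording contradiction: SAP 8.2.1, the heading, the code variable name and the responder table all point to change or improvement. The code name alone does not settle it, since SAP 8.6.1 lets code be modified without an amendment.
- A reader might infer that the remission rate was silently removed. The SAP history lists changes made in V2.0, not departures from the protocol; V1.0 is not available, and the table list and templates appear by title only. The absence is established for the readable text alone.

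The Marsh 0–1 rate does not replace the missing one, because Protocol 22.6 lists both.

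**Conclusion.** The point holds as a discrepancy between protocol and SAP, together with a weak choice of lead scale and a contradictory outcome definition. The protocol's VH:CD > 2 rate is absent from the readable SAP text. The 30% table in its place has no protocol basis or rationale, and below a baseline of 1.54 it can count subjects who do not reach 2. Those statements rest on the documents and arithmetic alone.

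The lead relative-change analysis is undefined at 0, can be unstable near 0, and does not match SAP section 2. The share of the 30% rate due to error cannot be sized. Under constant additive error of SD 0.1–0.2 it is about 34–42% at a baseline of 0.2 and 2–14% at 1.0; under proportional error there is no excess at low baselines. The reduction/change conflict affects the sign of the estimate and its interval for VH:CD and total IEL, not the p-value. This should be corrected before unblinding, but it does not threaten the primary analysis.

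**What to change.** 1. Restore the percentage of subjects with VH:CD > 2, counted among those with baseline ≤ 2, as the protocol-specified responder table. Keep the 30% table as supportive.
2. Make the already planned absolute-change ANCOVA the lead VH:CD analysis and report relative change as supportive.
3. Define Y as post minus pre for VH:CD and total IEL (divided by pre where relative), and state that higher VH:CD and lower IEL counts are better.

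The cost is SAP wording and one extra frequency table; no new modelling is needed. The downside is that the 30% and relative-change results become supportive. The threshold of 2 has its own noise for subjects already near it: with symmetric error, a true value of exactly 2 reads above 2 about half the time. That is a reason to show both tables.
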